## 10. MEASUREMENT OF EFFECT

For the purposes of this study, patients should be reevaluated for response every 2 cycles (1 cycle = 6 weeks). In addition to a baseline scan, confirmatory scans should also be obtained 6 weeks following initial documentation of objective response.

### 10.1 Definitions

Response and progression will be evaluated in this study using the new international criteria proposed by the Response Evaluation Criteria in Solid Tumors (RECIST) Committee [*JNCI* 92(3):205-216, 2000]. Changes in only the largest diameter (unidimensional measurement) of the tumor lesions are used in the RECIST criteria. Note: Lesions are either measurable or non-measurable using the criteria provided below. The term “evaluable” in reference to measurability will not be used because it does not provide additional meaning or accuracy.

#### 10.1.1 Measurable disease

Measurable lesions are defined as those that can be accurately measured in at least one dimension (longest diameter to be recorded) as >20 mm with conventional techniques (CT, MRI, x-ray) or as >10 mm with spiral CT scan. All tumor measurements must be recorded in millimeters (or decimal fractions of centimeters).

#### 10.1.2 Non-measurable disease

All other lesions (or sites of disease), including small lesions (longest diameter <20 mm with conventional techniques or <10 mm using spiral CT scan), are considered non-measurable disease. Bone lesions, leptomeningeal disease, ascites, pleural/pericardial effusions, lymphangitis cutis/pulmonis, inflammatory breast disease, abdominal masses (not followed by CT or MRI), and cystic lesions are all non-measurable.

#### 10.1.3 Target Lesions

All measurable lesions up to a maximum of five lesions per organ and 10 lesions in total, representative of all involved organs, should be identified as target lesions and recorded and measured at baseline. Target lesions should be selected on the basis of their size (lesions with the longest diameter) and their suitability for accurate repeated measurements (either by imaging techniques or clinically). A sum of the longest diameter (LD) for all target lesions will be calculated and reported as the baseline sum LD. The baseline sum LD will be used as reference by which to characterize the objective tumor response.

#### 10.1.4 Non-target Lesions

All other lesions (or sites of disease) should be identified as **non-target lesions** and should also be recorded at baseline. Non-target lesions include measurable lesions that exceed the maximum numbers per organ or total of all involved organs as well as non-measurable lesions. Measurements of these lesions are not required, but the presence or absence of each should be noted throughout follow-up.

## 10.2 Guidelines for Evaluation of Measurable Disease

All measurements should be taken and recorded in metric notation using a ruler or calipers. All baseline evaluations should be performed as closely as possible to the beginning of treatment and never more than 4 weeks before the beginning of the treatment.

**Note:** Tumor lesions that are situated in a previously irradiated area are only considered measurable if there has been documented growth of these lesions prior to study.

The same method of assessment and the same technique should be used to characterize each identified and reported lesion at baseline and during follow-up. Imaging-based evaluation is preferred to evaluation by clinical examination when both methods have been used to assess the antitumor effect of a treatment.

**Clinical lesions.** Clinical lesions will only be considered measurable when they are superficial (e.g., skin nodules and palpable lymph nodes). In the case of skin lesions, documentation by color photography, including a ruler to estimate the size of the lesion, is recommended.

**Chest x-ray.** Lesions on chest x-ray are acceptable as measurable lesions when they are clearly defined and surrounded by aerated lung. However, CT is preferable.

**Conventional CT and MRI.** These techniques should be performed with cuts of 10 mm or less in slice thickness contiguously. Spiral CT should be performed using a 5 mm contiguous reconstruction algorithm. This applies to tumors of the chest, abdomen, and pelvis. Head and neck tumors and those of extremities usually require specific protocols.

**Ultrasound (US).** When the primary endpoint of the study is objective response evaluation, US should not be used to measure tumor lesions. It is, however, a possible alternative to clinical measurements of superficial palpable lymph nodes, subcutaneous lesions, and thyroid nodules. US might also be useful to confirm the complete disappearance of superficial lesions usually assessed by clinical examination.

**Endoscopy, Laparoscopy.** The utilization of these techniques for objective tumor evaluation has not yet been fully and widely validated. Their uses in this specific context require sophisticated equipment and a high level of expertise that may only be available in some centers. Therefore, the utilization of such techniques for objective tumor response should be restricted to validation purposes in reference centers. However, such techniques may be useful to confirm complete pathological response when biopsies are obtained.

**Tumor markers.** Tumor markers alone cannot be used to assess response. If markers are initially above the upper normal limit, they must normalize for a patient to be considered in complete clinical response. Specific additional criteria for standardized usage of prostate-specific antigen (PSA) and CA-125 response in support of clinical trials are being developed.

**Cytology, Histology.** These techniques can be used to differentiate between partial responses (PR) and complete responses (CR) in rare cases (e.g., residual lesions in tumor types, such as germ cell tumors, where known residual benign tumors can remain).

*The cytological confirmation of the neoplastic origin of any effusion that appears or worsens during treatment when the measurable tumor has met criteria for response or stable disease is mandatory to differentiate between response or stable disease (an effusion may be a side effect of the treatment) and progressive disease.*

## 10.3 Response Criteria

### 10.3.1 Evaluation of target lesions

Complete Response (CR):	Disappearance of all target lesions
Partial Response (PR):	At least a 30% decrease in the sum of the longest diameter (LD) of target lesions, taking as reference the baseline sum LD
Progressive Disease (PD):	At least a 20% increase in the sum of the LD of target lesions, taking as reference the smallest sum LD recorded since the treatment started or the appearance of one or more new lesions
Stable Disease (SD):	Neither sufficient shrinkage to qualify for PR nor sufficient increase to qualify for PD, taking as reference the smallest sum LD since the treatment started

### 10.3.2 Evaluation of non-target lesions

Complete Response (CR):	Disappearance of all non-target lesions and normalization of tumor marker level
Incomplete Response/ Stable Disease (SD):	Persistence of one or more non-target lesion(s) and/or maintenance of tumor marker level above the normal limits
Progressive Disease (PD):	Appearance of one or more new lesions and/or unequivocal progression of existing non-target lesions

Although a clear progression of “non-target” lesions only is exceptional, in such circumstances the opinion of the treating physician should prevail, and the progression status should be confirmed at a later time by the review panel (or study chair).

Note: If tumor markers are initially above the upper normal limit, they must normalize for a patient to be considered in complete clinical response.

### 10.3.3 Evaluation of best overall response

The best overall response is the best response recorded from the start of the treatment until disease progression/recurrence (taking as reference for progressive disease the smallest measurements recorded since the treatment started). The patient's best response assignment will depend on the achievement of both measurement and confirmation criteria (see Sections 10.3.1 and 10.4.1).

Target Lesions	Non-Target Lesions	New Lesions	Overall Response
CR	CR	No	CR
CR	Incomplete response/SD	No	PR
PR	Non-PD	No	PR
SD	Non-PD	No	SD
PD	Any	Yes or No	PD
Any	PD	Yes or No	PD
Any	Any	Yes	PD

Note:

- X Patients with a global deterioration of health status requiring discontinuation of treatment without objective evidence of disease progression at that time should be classified as having “symptomatic deterioration.” Every effort should be made to document the objective progression, even after discontinuation of treatment.
- X In some circumstances, it may be difficult to distinguish residual disease from normal tissue. When the evaluation of complete response depends on this determination, it is recommended that the residual lesion be investigated (fine needle aspirate/biopsy) before confirming the complete response status.

## 10.4 Confirmatory Measurement/Duration of Response

### 10.4.1 Confirmation

To be assigned a status of PR or CR, changes in tumor measurements must be confirmed by repeat assessments that should be performed 6 weeks after the criteria for response are first met. In the case of SD, follow-up measurements must have met the SD criteria at least once after study entry at a minimum interval 12 weeks (see section 10.3.3).

### 10.4.2 Duration of overall response

The duration of overall response is measured from the time measurement criteria are met for CR or PR (whichever is first recorded) until the first date that recurrent or progressive disease is objectively documented (taking as reference for progressive disease the smallest measurements recorded since the treatment started).

The duration of overall CR is measured from the time measurement criteria are first met for CR until the first date that recurrent disease is objectively documented.

#### 10.4.3 Duration of stable disease

Stable disease is measured from the start of the treatment until the criteria for progression are met, taking as reference the smallest measurements recorded since the treatment started. The maintenance of stable disease or objective response for 6 months or greater is defined as prolonged stable disease.

### 10.5 Progression-Free Survival

Progression-free survival (PFS) is defined as the duration of time from start of treatment to time of progression.

### 10.6 Response Review

All responses will be reviewed, independently from the investigators, by a staff radiologist. Staff with the Princess Margaret Hospital Phase II Consortium will conduct a simultaneous review of the patients' files and radiological images.

## 11. DATA REPORTING / REGULATORY CONSIDERATIONS

Adverse event lists, guidelines, and instructions for AE reporting can be found in Section 7.0 (Adverse Events: List and Reporting Requirements).

### 11.1 Data Reporting

#### 11.1.1 Method

This study will be monitored by the Clinical Data Update System (CDUS) version 3.0. Cumulative CDUS data will be submitted quarterly to CTEP by electronic means. Reports are due January 31, April 30, July 31, and October 31. Instructions for submitting data using the CDUS can be found on the CTEP web site (<http://ctep.cancer.gov/reporting/cdus.html>).

#### 11.1.2 Responsibility for Submissions

Study participants are responsible for submitting CDUS data and/or data forms to the Coordinating Center quarterly by January 31, April 30, July 31, and October 31 to allow time for Coordinating Center compilation, Principal Investigator review, and timely submission to CTEP (see Section 11.1.1.). Please refer to Appendix H, Data

Management Guidelines, for further details regarding data submission requirements.

The Coordinating Center is responsible for compiling and submitting CDUS data to CTEP for all participants and for providing the data to the Principal Investigator for review.

## **11.2 CTEP Multicenter Guidelines**

This protocol will adhere to the policies and requirements of the CTEP Multicenter Guidelines. The specific responsibilities of the Principal Investigator and the Coordinating Center (Study Coordinator) and the procedures for auditing are presented in Appendix I.

The Principal Investigator/Coordinating Center is responsible for distributing all IND Action Letters or Safety Reports received from CTEP to all participating institutions for submission to their individual IRBs for action as required.

Except in very unusual circumstances, each participating institution will order DCTD-supplied agents directly from CTEP. Agents may be ordered by a participating site only after the initial IRB approval for the site has been forwarded by the Coordinating Center to the CTEP PIO ([[contact]](mailto:[contact])) except for Group studies.

## **11.3 Cooperative Research and Development Agreement (CRADA)/Clinical Trials Agreement (CTA)**

The agent(s), supplied by CTEP, DCTD, NCI, used in this protocol is/are provided to the NCI under a Collaborative Agreement (CRADA, CTA) between the Pharmaceutical Company(ies) [hereinafter referred to as ACollaborator(s)@] and the NCI Division of Cancer Treatment and Diagnosis. Therefore, the following obligations/guidelines, in addition to the provisions in the AIntellectual Property Option to Collaborator@ (<http://ctep.cancer.gov/industry>) contained within the terms of award, apply to the use of Agent(s) in this study:

1. Agent(s) may not be used for any purpose outside the scope of this protocol, nor can Agent(s) be transferred or licensed to any party not participating in the clinical study. Collaborator(s) data for Agent(s) are confidential and proprietary to Collaborator(s) and shall be maintained as such by the investigators. The protocol documents for studies utilizing investigational agents contain confidential information and should not be shared or distributed without the permission of the NCI. If a copy of this protocol is requested by a patient participating on the study or patient's family member, the individual should sign a confidentiality agreement. A suitable model agreement can be downloaded from <http://ctep.cancer.gov>.
2. For a clinical protocol where there is an investigational Agent used in combination with (an)other investigational Agent(s), each the subject of different collaborative agreements, the access to and use of data by each Collaborator shall be as follows (data pertaining to such combination use shall hereinafter be referred to as "Multi-Party Data".):

- a. NCI must provide all Collaborators with prior written notice regarding the existence and nature of any agreements governing their collaboration with NIH, the design of the proposed combination protocol, and the existence of any obligations that would tend to restrict NCI's participation in the proposed combination protocol.
  - b. Each Collaborator shall agree to permit use of the Multi-Party Data from the clinical trial by any other Collaborator solely to the extent necessary to allow said other Collaborator to develop, obtain regulatory approval, or commercialize its own investigational agent.
  - c. Any Collaborator having the right to use the Multi-Party Data from these trials must agree in writing prior to the commencement of the trials that it will use the Multi-Party Data solely for development, regulatory approval, and commercialization of its own investigational agent.
3. Clinical Trial Data and Results and Raw Data developed under a collaborative agreement will be made available exclusively to Collaborator(s), the NCI, and the FDA, as appropriate and unless additional disclosure is required by law or court order.—Additionally, all Clinical Data and Results and Raw Data will be collected, used and disclosed consistent with all applicable federal statutes and regulations for the protection of human subjects, including, if applicable, the *Standards for Privacy of Individually Identifiable Health Information* set forth in 45 C.F.R. Part 164.
4. When a Collaborator wishes to initiate a data request, the request should first be sent to the NCI, who will then notify the appropriate investigators (Group Chair for Cooperative Group studies, or PI for other studies) of Collaborator's wish to contact them.
5. Any data provided to Collaborator(s) for phase 3 studies must be in accordance with the guidelines and policies of the responsible Data Monitoring Committee (DMC), if there is a DMC for this clinical trial.
6. Any manuscripts reporting the results of this clinical trial must be provided to CTEP for immediate delivery to Collaborator(s) for advisory review and comment prior to submission for publication. Collaborator(s) will have 30 days from the date of receipt for review. Collaborator shall have the right to request that publication be delayed for up to an additional 30 days in order to ensure that Collaborator's confidential and proprietary data, in addition to Collaborator(s)'s intellectual property rights, are protected. Copies of abstracts must be provided to CTEP for forwarding to Collaborator(s) for courtesy review as soon as possible and preferably at least three (3) days prior to submission, but in any case, prior to presentation at the meeting or publication in the proceedings. Press releases and other media presentations must also be forwarded to CTEP prior to release. Copies of any manuscript, abstract, and/or press release/ media presentation should be sent to:

Regulatory Affairs Branch, CTEP, DCTD, NCI  
[name]  
[name]  
[contact]  
E-mail: [[contact]](mailto:[contact])

The Regulatory Affairs Branch will then distribute them to Collaborator(s). No publication, manuscript or other form of public disclosure shall contain any of Collaborator's confidential/proprietary information.

## 12. STATISTICAL CONSIDERATIONS

Adverse event lists, guidelines, and instructions for AE reporting can be found in Section 7.0 (Adverse Events: List and Reporting Requirements).

### 12.1 Study Design/Endpoints

The primary endpoint of the study is objective response rate (ORR). ORR is defined as the rate of complete or partial response as defined by the RECIST criteria (see section 10.3). Secondary endpoints will include prolonged stable disease (as defined in sections 1 and 11.4.3) overall survival, toxicity and time to progression.

A two-stage design has been adopted for this study that judges the agent as promising based on tumor response rate. An objective response rate of 20% would be considered of interest, whereas a rate of 5% would be deemed uninteresting. For this design we will set  $\alpha \approx 0.05$  and  $\beta \approx 0.20$ .

- In the first stage, 15 patients will be accrued. If no objective responses are observed among the initial 15 evaluable patients, the study would be terminated early and declared negative.
- If there are 1 or more objective responses, the trial will continue on to a second stage, accruing an additional 15 patients.
- If at least 4 objective responses (at least 13%) are observed among the 30 evaluable patients, this agent would be considered worthy of further testing in this disease.

This design yields 86.5% (type II error=0.135) power to detect a true objective response rate of at least 20% and 0.942 (type I error=0.058) probability of a negative result if the true objective response rate is no more than 5%. The probability of stopping at the end of the first stage is approximately 0.46 and the expected sample size is 23.05 if the true objective response rate is 5%.

Data from clinical trials of single-agent chemotherapy in the salvage setting for endometrial cancer suggest a median progression-free survival from 1.8 – 3.2 months (see section 2). Assuming exponential survival, this equates to an approximate 6-month progression-free survival rate of 10-25%. Based on these statistics, we consider 6-month stable disease rate of greater than 25% (or 4 out of the first 15 patients) to be of interest, even in the absence of

objective response.

If, at the end of stage I, no objective responses are seen, but at least 4 patients demonstrate prolonged stable disease (i.e. best response of stable disease that is maintained for at least 6 months), consideration would be given to continuing accrual to the second stage. In this circumstance, a decision to continue to stage II would only be made in consultation with CTEP.

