## **Phase 1 Experience**

In an early phase 1 study designed to investigate dosing regimen and scheduling (in human subjects, the results of clinical pharmacology studies demonstrate that Cmax and AUC increased in a proportional manner after single doses of 50 to 350mg as well as after multiple doses of 25 to 100 mg), 41 patients with a variety of advanced solid tumors received sunitinib administered on a schedule of 2 weeks of treatment followed by 2 weeks off (2/2 schedule) or 4 weeks on with 2 weeks off (4/2 schedule) 21. Doses evaluated on the 2/2 schedule (n=23) included 50 mg every other day (n=3), 50 mg daily (n=15), or 75 mg daily (n=5); the 18 patients enrolled in the 4/2 schedule received 25 mg daily (n=3) or 50 mg daily (n=15). The most frequent adverse events (AEs) were constitutional (fatigue/asthenia), gastrointestinal (nausea, vomiting, diarrhea) and hematologic (neutropenia, thrombocytopenia). Most of the AEs were grade 1 or 2, although at 75 mg daily, grade 3 and 4 fatigue/asthenia were dose limiting but readily reversible on discontinuation of treatment. There were 4 partial responses (PRs) assessed by RECIST and 22 patients with stable disease (SD) among the 41 patients.

A phase 1 dose-escalation study in 28 patients with advanced tumors evaluated sunitinib doses of 30 mg/m^2 every other day, and doses of 30, 42, or 59 mg/m^2 daily on the 4/2 schedule 22. Grade 3 fatigue and hypertension were dose limiting at 59 mg/m^2 as well as grade 2 bullous skin toxicity, and the MTD was defined as 42 mg/m^2 daily. Based on these and other reversible AEs in the 12 patients treated at the MTD, the recommended phase 2 dose on the 4/2 schedule was determined to be 50 mg/day. Responses determined by RECIST were seen in 6 of 23 evaluable patients (RCC, NET, gastrointestinal stromal tumors, and unknown primary). Tumor responses in patients treated at higher doses were often associated with reduced intratumoral vascularization and central tumor necrosis, leading to organ perforation in one patient and fistula in another. These observations suggest the possible necessity for careful tumor density monitoring to detect early evidence of necrosis.

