Preliminary data from a pivotal multinational, randomized (2:1), double-blind, placebo-controlled phase 3 trial in over 300 patients with imatinib-resistant GIST were presented at a national meeting in May 2005 17. Patients on the active treatment arm received sunitinib at a dose of 50 mg daily on the 4/2 schedule. At the time of the interim analysis, the study was unblinded based on the independent core laboratory efficacy assessment of the primary endpoint (TTP). The median TTP for the treatment arm (n=207) was 27.3 weeks compared to a median of 6.4 weeks for placebo (n=105) (p<0.001) (Investigator's Brochure SU011248, 2005).

In addition to patients with RCC and GIST, 106 patients with NET were treated on a phase 2 protocol with 50 mg sunitinib daily on schedule 4/2 28. Among the 52 evaluable patients with islet cell NET, there were 7 PRs (1 unconfirmed), 40 SD, and 3 PD, while among the 39 evaluable carcinoid NET patients, there were 2 PRs (1 unconfirmed), 36 SD, and 1 PD. Sunitinib is also under phase 2 evaluation in MBC, with 38 patients enrolled thus far 29. There have been 4 PR, 5 SD, and 14 PD among the 23 evaluable MBC patients on this ongoing trial.

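### Do the decision rules on 15 and 30 evaluable patients conflict with the all-eligible analysis in Section 12.4.2?

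*Combined protocol and SAP*

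**What the plan says.** The Schema and Section 12.1 state the rules on evaluable patients. The trial stops if there is no response among the first 15. The final rule in 12.1 begins "If at least 4 objective responses (at least 13%) are observed among the 30 evaluable patients", in which case the agent merits further testing.

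The same section also describes the stages as accruals of 15 and then 15 more patients, and Section 12.2 gives a sample size of 15 to a projected maximum of 30. Neither section allows for unassessed patients.

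Section 12.4.1 makes every treated patient evaluable for toxicity. Section 12.4.2 does not use the word. It places eligible patients in the main response analysis, with a possible exception for those who took no drug. It treats response categories 4 to 9, which include early deaths and unknown response, as failures. It bases all conclusions on eligible patients and bars subset analyses from supporting efficacy conclusions.

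Elsewhere *evaluable* appears in summaries of other sunitinib trials in Section 2.2:
- Phase 1: "A phase 1 dose-escalation study in 28 patients with advanced tumors", and later "Responses determined by RECIST were seen in 6 of 23 evaluable patients".
- Neuroendocrine tumours: "106 patients with NET were treated on a phase 2 protocol with 50 mg sunitinib daily on schedule 4/2", then "Among the 52 evaluable patients with islet cell NET" and "among the 39 evaluable carcinoid NET patients".
- Metastatic breast cancer: "There have been 4 PR, 5 SD, and 14 PD among the 23 evaluable MBC patients on this ongoing trial", "with 38 patients enrolled thus far".

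**The concern.** In each of those summaries the evaluable patients are fewer than those treated or enrolled: 23 of 28, 52 + 39 = 91 of 106, and 23 of 38. If the word carries that sense into Section 12.1, then 15 accrued patients will usually give fewer than 15 evaluable ones, and the team might keep enrolling until 30 have been assessed. Section 12.4.2 would then analyse more than 30 eligible patients, for whom the plan gives no cutoff.

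Unassessed patients are also foreseeable here. The first routine response scan comes after two six-week cycles, while Section 2.1 reports that most second-line patients progress within 3 months.

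The verdict could depend on the reading. Suppose 35 eligible patients are treated, 5 of the first 30 are never assessed, and there are 4 responders, at least one of them among the first 15 and exactly one among patients 31 to 35. The first 30 eligible patients hold 3 responders, which is a negative result. The 30 assessed patients hold 4, which is a positive one. A choice of that kind, made after responses are known, would matter for the primary endpoint.

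**Working it through.** **1. Reproduce the plan's figures.** Inputs from Section 12.1: stages of 15 + 15, stop at 0/15, positive at 4 or more of 30, rates 5% and 20%. With b the binomial probability,

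P(positive) = Σ over x = 1 to 15 of b(x; 15, p) × P[Bin(15, p) ≥ 4 − x].

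- p = 0.05: 0.0582 (stated 0.058).
- p = 0.20: 0.8649 (stated 86.5%).
- Early stopping at 5%: 0.95^15 = 0.463 (stated 0.46).
- Expected size at 5%: 15 + 15 × (1 − 0.463) = 23.05 (stated 23.05).

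All four agree when the denominators are exactly the 15 and 30 patients that Sections 12.1 and 12.2 accrue.

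**2. Size the rival reading.** The plan gives no unassessed share d for this trial, so d is an assumption taken from Section 2.2:
- Neuroendocrine trial: (106 − 91)/106 = 0.142.
- Phase 1 trial: (28 − 23)/28 = 0.179.
- Acute myeloid leukaemia dose-escalation study: 4 patients with mutations plus 10 evaluable wild-type patients, out of 15 enrolled, so d = 1/15 = 0.067. Response there is not by RECIST.

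Patients needed for 30 assessed, 30/(1 − d): 32.1 (d = 0.067), 34.9 (0.142), 36.5 (0.179).

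Let p be the response rate among all eligible patients. The rate among assessed patients is then p/(1 − d). If nobody is ineligible, the responders among the first 30 eligible are a subset of those among the first 30 assessed. The probability of opposite verdicts is therefore the difference between P(positive) at p/(1 − d) and at p.

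| p | P(positive), first 30 eligible | d = 0.067: assessed (difference) | d = 0.142 | d = 0.179 |
|---|---|---|---|---|
| 0.05 | 0.058 | 0.071 (0.013) | 0.091 (0.032) | 0.103 (0.044) |
| 0.10 | 0.341 | 0.391 (0.050) | 0.455 (0.114) | 0.490 (0.149) |
| 0.20 | 0.865 | 0.900 (0.035) | 0.934 (0.069) | 0.948 (0.083) |

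The 0.091 and 0.103 in the first row are type I errors only if the 5% null is a rate among all eligible patients while the rule is applied to assessed patients. With one population for both, the figure is 0.058.

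**3. Set the texts side by side.** The rival reading comes only from accounts of other trials. This plan's own sections point the other way:
- Section 12.4.2 says who supports the conclusions and what happens to a patient with unknown response: that patient counts as a failure.
- Sections 12.1 and 12.2 count 15 + 15 = 30 accrued patients.
- No section provides for replacing an unassessed patient.
- Section 12.4.1 uses the word for every treated patient.
- Section 10.1 declines to use it when describing measurability.

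The background usage is not uniform either. The 52 evaluable islet-cell patients are listed as 7 PR + 40 SD + 3 PD = 50, so in that trial evaluable does not coincide with assigned a response. The breast cancer trial was still enrolling, so 23 of 38 may only reflect timing.

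**The case for a change.** The strongest case for a change is that the undefined word governs both the stage I stop and the final verdict. Section 12.4.2 says who is analysed but not when accrual ends, and 30 is only a projected maximum. One cross-reference would close the gap at no cost. It is true that the word is undefined and that a cross-reference would be tidier. But it would only write down what Section 12.4.2 already implies, and no size, cutoff or stated error rate would move.

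A second argument is that counting unassessed patients as failures costs power if 20% was meant as a rate among assessed patients. That is correct. At p = 0.20 × (1 − d), power is 0.800 for an assumed d of 10%, 0.767 for 14.2% and 0.735 for 17.9%, against a design target of about 0.80. In return, type I error falls to 0.042, 0.037 and 0.032. This is the usual conservative convention, and the plan states it openly. Replacing unassessed patients instead would be a different design, with about 35 to 37 enrolled at the two larger shares. Choosing between the two is a trade-off.

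A third argument is that the ambiguity can only favour the drug. That holds only if every enrolled patient is eligible. An ineligible but assessed non-responder could take one of the 30 evaluable places and push a later responder out, reversing the direction. Section 4.2 requires all eligibility criteria to be met at registration, so this should be rare.

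**Conclusion.** The concern identifies an undefined word, not a contradiction. Taking *evaluable* in the Schema and Section 12.1 as the Section 12.4.2 set (eligible patients who started sunitinib, categories 4 to 9 as non-responders) makes the counts agree however many patients go unassessed. The stated 0.058, 86.5%, 0.46 and 23.05 are then all correct. Patients who are registered but never treated are the one loose end in that set, and Section 4.1 already allows their registration to be cancelled.

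The chance of opposite verdicts, 0.01 to 0.04 at a 5% true rate, 0.05 to 0.15 at 10% and 0.03 to 0.08 at 20%, arises only if the team departs from Section 12.4.2 and replaces unassessed patients. It also rests on unassessed shares of 7% to 18% carried over from other trials and on no ineligible enrolment. An analyst following the plan as written, with Section 12.4.2 governing, reaches a sound result, so no change is needed.
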